Quantitative analysis of the participatory ranking exercise: Each participant's responses will be used to generate an individualized weighted composite outcome. We will consider a utility function that is a weighted combination of the individual endpoints specified by each participant, with weights determined by the patient's preferences as proposed in Butler et al.¹⁶ The patient's preference weights will be scaled to sum to 1, such that the patient-specific outcome will be a convex combination of the eligible outcomes. With the weighted utility function, we then define potentially counterfactual treatment effects, defined as the expected utility function under the four different treatment exposures. The optimal individual treatment rule is defined as in Qian and Murphy¹⁷ as the treatment that maximizes the expected utility function.

We will then use the composite outcomes generated using the participator ranking exercise (see above) in a study that uses de-identified data within OLDW. Specifically, we will emulate a target trial comparing the effectiveness of GLP1-RA, SGLT2i, DPP-4i, and SU classes with respect to each of these patient-specified composite outcomes. The target parameter will be the six pairwise differences in the personalized utility function between the drug classes. We provide an overview of that analysis below, though all analyses using

OLDW data have been previously deemed exempt from IRB review as all data is statistically de-identified by OptumLabs prior to being made available to researchers.

Primary analyses will be conducted under an intention-to-treat approach, modified to define “intention” as a patient having two consecutive fills of the assigned drug. All patients will continue follow-up and complete all outcome assessments until the planned conclusion of the study or end of observation in OLDW.

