We will estimate multinomial propensity score models using data from 12 months prior to the index date to account for the multiple treatments.¹⁸ Predictions from the estimated propensity score model can be used for inverse probability weighting (IPW) to emulate baseline randomization. We will allow for flexible modeling strategies with controls to assess for overfitting. Our proposal is to use the super learner framework¹⁹ with a diverse set of individual prediction algorithms included in the ensemble. The super learner framework allows for flexible estimation of an ensemble predictor with the theoretical properties of cross-validation for model selection to control for overfitting. The framework has been demonstrated to outperform individual algorithms for the estimation of propensity scores.^{20,21} The distribution of the predicted propensity scores will be evaluated for evidence of violations of the positivity assumption. For moderate violations of positivity, the propensity scores will be truncated at 0.01 and 0.99 to control inflation of the standard errors. Our intention is to use the entire distribution of OLDW as our population of interest, but if more extreme positivity violations are observed, the reference population will be narrowed to a realistic treatment intervention population.

The proposed IPW weight with multinomial treatment groups is unstabilized, as our primary estimand is the population average treatment effect.²² If weights have extreme values when evaluating the distributions, then the stabilized version using the denominator proposed in Yoshida²³ for the optimal matching stabilized weights with multiple treatments will be used as a sensitivity analysis to avoid large confidence intervals for the effect estimates. The final propensity scores will then be incorporated as IPWs into a time-to-event model. If the proportional hazards assumptions hold, this will be a Cox model; otherwise, we will use Akaike Information Criteria to identify the best parametric time-to-event specification for the data. For the final model, we will report model diagnostic and performance statistics, and either hazard or time ratios with 95% confidence intervals. A single model with all treatment groups will be estimated and the omnibus test for at least one treatment group having a different cumulative incidence rate will be evaluated. If that test is statistically significant, then each pairwise comparison will be tested and pairwise effects estimated.

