The targeted learning algorithm for the causal hazard rate as defined in Moore and van der Laan²⁴ will be implemented to estimate the four treatment hazard rates and the corresponding hazard ratios or time ratios, according to the model specification, will be estimated for each of the 6 pairwise comparisons between treatment groups. A single overall omnibus test for the four hazard rates being equal to each other versus at least one different will be conducted at the 0.05 significance level, with pairwise comparison p-values adjusted using the Holm closed sequential multiple testing procedure.^{25,26}

Predefined subgroup analyses for heterogeneity of treatment effects (HTE) will be evaluated for the following characteristics: sex (female vs. male), race/ethnicity (Black, Hispanic, Asian, other vs. White), and age (45-64, 65-74, ≥ 75 vs. <45 years). While there is no definitive evidence of HTE by these characteristics, the incidence of CVD and kidney disease outcomes are known to vary²⁷⁻³⁰ and may be mediated by different responses to therapeutic interventions. We will also assess for HTE as a function of different levels of underlying CVD risk, as the examined drugs may be more effective at reducing the risks of primary and secondary endpoints among patients at higher risk for these events or with certain CVD risk factors already present.^{31-35 36-39} The primary model will be used to estimate treatment effects across subgroups, with the targeted parameter for the subgroup analysis being the difference in the predicted treatment effect for each pairwise comparison between the

subgroups.⁴⁰ We will estimate multivariable effect prediction models^{41,42} to assess for HTE between the predefined subgroups by incorporating specific parameters for the statistical interaction effect between the treatment and subgroup variables.^{36,37} Propensity score weights will be used to emulate randomization according to the target trial framework. Internal cross-validation will be used to control for overfitting of the prediction model.⁴³ Adjustment for multiple testing will be done accounting for the total number of predefined HTE analyses.

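### Optional improvement, not an error: with four drug classes, Holm's second and third divisors (5 and 4) can both be 3 while the 0.05 family-wise bound still holds

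*Combined protocol and SAP*

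**What the plan says.** All the relevant text is in the Data Analysis Plan, in the overview of the OLDW analysis.

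- The paragraph on weights and the time-to-event model fits all four classes together: "A single model with all treatment groups will be estimated". The estimand is the average effect in one population, although after severe positivity violations "the reference population will be narrowed to a realistic treatment intervention population".
- The same paragraph makes the pairwise tests conditional on an overall test: "the omnibus test for at least one treatment group having a different cumulative incidence rate will be evaluated". It continues: "If that test is statistically significant, then each pairwise comparison will be tested and pairwise effects estimated".
- The targeted-learning paragraph restates the overall test, now for hazard rates and at the 0.05 level: "A single overall omnibus test for the four hazard rates being equal to each other versus at least one different will be conducted". The pairwise rule follows: "with pairwise comparison p-values adjusted using the Holm closed sequential multiple testing procedure".

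No divisors are printed, and the plan does not mention using the logical links among the six comparisons.

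**The concern.** Holm's rule works for any six hypotheses, related or not. After one rejection it allows for five true nulls among those left, and after two rejections for four. Six equalities among four classes are not unrelated: if A equals B and B equals C, then A equals C. Some of the states that Holm allows for therefore cannot occur, and the second and third cut-offs are lower than they need to be.

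No false-positive problem arises. What is at stake is power. A real difference between two classes may go undeclared, in a study meant to help patients and clinicians choose among those classes.

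**Working it through.** **Inputs from the plan.** Four classes, six pairwise comparisons, level 0.05, Holm adjustment, one model. Two-sided tests are assumed, since sidedness is not stated.

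**Family size.** C(4,2) = 6, as the plan says. Ordinary Holm divisors are 6 − j + 1 at step j, giving 6, 5, 4, 3, 2, 1.

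**How many equalities can be true together.** There are 15 ways to group four classes by equal effect:

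| Grouping | Number of ways | True equalities |
|---|---|---|
| all four equal | 1 | 6 |
| three equal, one apart | 4 | C(3,2) = 3 |
| two pairs | 3 | 2 |
| one pair, two singles | 6 | 1 |
| all different | 1 | 0 |

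Five or four true equalities never occur. The most that can still be true after 0, 1, 2, 3, 4 and 5 correct rejections is 6, 3, 3, 3, 2 and 1.

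**Cut-offs.**

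| Step | Holm | Revised |
|---|---|---|
| 1 | 0.05/6 = 0.0083 | 0.0083 |
| 2 | 0.05/5 = 0.0100 | 0.05/3 = 0.0167 |
| 3 | 0.05/4 = 0.0125 | 0.05/3 = 0.0167 |
| 4 | 0.05/3 = 0.0167 | 0.0167 |
| 5 | 0.05/2 = 0.0250 | 0.0250 |
| 6 | 0.0500 | 0.0500 |

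**Why the bound holds.** Consider the first true equality to be rejected.
- If all six are true, it is rejected at step 1, at 0.05/6. Bonferroni over six gives at most 0.05.
- If three are true, at most three false ones precede it, so it falls at step 4 or earlier, where the divisor is at least 3. Bonferroni over three gives at most 0.05.
- If two are true, the divisor is at least 2. If one is true, it is at least 1. The bound is again 0.05.

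This needs valid p-values but no assumption about correlation or equal precision, and it holds with or without the omnibus gate. No revised divisor exceeds Holm's, so every Holm rejection is kept.

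**Worked case** (assumed equal-variance estimates). Ordered p-values are 0.004, 0.012, 0.015, 0.65, 0.71, 0.94. The omnibus p is 0.015, so the gate is passed. Holm rejects the first (0.004 < 0.0083) and stops at the second (0.012 > 0.0100). The revised rule rejects three (0.012 and 0.015 are both below 0.0167) and stops at 0.65.

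**Size of the gain.** Simulation used 400,000 replicates per setting, with independent normal class estimates. NCP is the pairwise difference divided by its standard error. Gains are percentage points of average power per true difference, revised minus Holm, without the gate.

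| Pattern (equal SEs assumed) | Gain at each NCP |
|---|---|
| one class different | +0.6 (1), +2.7 (2), +3.7 (2.5), +3.5 (3), +1.3 (4), +0.2 (5) |
| two pairs | +2.7 (2), +3.1 (2.5), +2.4 (3), +0.5 (4), 0.0 (5) |
| equally spaced, adjacent NCP | +0.7 (0.5), +2.3 (1), +1.7 (1.5), +0.3 (2), 0.0 (2.5 and 3) |

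Equal precision is not assured, since "The proposed IPW weight with multinomial treatment groups is unstabilized". With assumed SEs of 0.5, 0.7, 1.0 and 1.5, gains were +2.1 to +3.8 in six settings. Keeping the omnibus gate changes the gains by only about 0.3 points.

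**Realised family-wise error.** With all classes equal it is 0.041 under both rules. With one class different at NCP 2 it rises from 0.029 to 0.040. With very large effects it is the same under both: 0.044, 0.049 and 0.050 for three, two and one true nulls.

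**What these NCPs mean as hazard ratios.** HR = exp(−NCP × √(2/events per class)), with no inflation from weighting.
- Assumed 1,000 events per class: NCP 2 gives exp(−0.089) = 0.91, and NCP 3 gives exp(−0.134) = 0.87.
- Assumed 10,000 events per class: 0.97 and 0.96.

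**The case against.** Holm as planned is valid and widely recognised, and nothing in the documents is contradicted. Preferring a sharper valid rule is an improvement at most. That stands, and it sets the ceiling on this point.

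The baseline is inferred. The plan prints no divisors and uses the word *closed*. A full closed test that exploits the logical links would do at least as well as 6, 3, 3, 3, 2, 1, and the gain would then be nil. However, ordinary Holm is itself a closed procedure and is the one named, so 6, 5, 4, 3, 2, 1 is the natural reading. The ambiguity is one more reason to print the rule.

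The OLDW text is offered only as an overview, and step-down divisors are fine detail for it. The point also leaves aside the stated target: "The target parameter will be the six pairwise differences in the personalized utility function between the drug classes". Both remarks are fair. The argument covers the hazard-ratio or time-ratio tests within one composite outcome. It does not address the utility differences or multiplicity across composites. If alpha were split across composites, the cut-offs would shrink, but the same divisors would apply to the smaller alpha.

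The gain is under 4 points, near zero for very small or large effects, and of unknown practical worth. Realised error also rises within the bound, so Holm's slack is used up. Both stand. The 0.05 bound presumes valid p-values after data-driven model choice, but Holm presumes the same.

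**Conclusion.** The point holds as an optional improvement of small worth. The plan as written controls family-wise error at 0.05. Divisors 6, 3, 3, 3, 2, 1 do so too and are never less powerful. The gain is about 0 to 4 percentage points per true difference in the settings simulated, largest at intermediate effects. A smallest p-value above 0.0083 still ends the procedure under either rule.

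The conclusion rests on one effect parameter per class, compared within one model, one population and one effect measure. If each pair were trimmed to its own population, equality would no longer carry over from pair to pair and the argument would fail. The power figures rest on assumed effects and standard errors, because the documents give neither event counts nor precision.

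**What to change.** State in the Data Analysis Plan, before results are seen, that the six ordered pairwise p-values are compared with 0.05/6, then 0.05/3 three times, then 0.05/2 and 0.05, stopping at the first failure. State that all six tests use one model, one effect measure and one common population, including when the reference population is narrowed. If *closed* was meant to denote another logically restricted procedure, name that one instead.

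Adjusted p-values follow directly: multiply each ordered p-value by its divisor, take the running maximum, and cap it at 1. In the worked case the first three become 0.024, 0.036 and 0.045, against 0.024, 0.060 and 0.060 under Holm.

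The cost is a sentence or two and no data. Realised error moves closer to 0.05 but not above it.

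A further step is possible but not needed. If one omnibus test at 0.05 of the same null, model, population and effect measure is made a binding gate, the first divisor can also be 3. The plan would first have to settle whether that test concerns cumulative incidence or hazard rates, since it says both. This variant gained 0 to 5.5 points over gated Holm. Against ungated 6, 3, 3, 3, 2, 1 it ranged from about −0.4 to +2.8 points in the settings tried, so it is not always better. It is safe only behind its gate: with all classes equal, family-wise error is 0.048 gated and 0.078 ungated.

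### Subgroup heterogeneity is assessed with interaction terms in a hazard- or time-ratio model, while the plan's target is a utility difference and the scale of the subgroup effect is not stated

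*Combined protocol and SAP*

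**What the plan says.** All of this is in the Data Analysis Plan.

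- **Target (quantitative analysis of the ranking exercise).** "The target parameter will be the six pairwise differences in the personalized utility function between the drug classes". Preference weights sum to 1, and "the patient-specific outcome will be a convex combination of the eligible outcomes". A utility difference is therefore a weighted sum of differences on the endpoint scales.
- **Outcome model (propensity-score and time-to-event paragraphs).** "The final propensity scores will then be incorporated as IPWs into a time-to-event model": Cox if proportional hazards holds, otherwise a parametric form chosen by AIC. The reported effects are "either hazard or time ratios with 95% confidence intervals". The targeted-learning step that follows also ends in hazard or time ratios.
- **Subgroups (HTE paragraph).** On the model: "The primary model will be used to estimate treatment effects across subgroups". The same sentence then sets the estimand, "with the targeted parameter for the subgroup analysis being the difference in the predicted treatment effect for each pairwise comparison", as a contrast of one subgroup against another. HTE is assessed with effect-prediction models "incorporating specific parameters for the statistical interaction effect between the treatment and subgroup variables". The subgroups are sex, race/ethnicity, age and levels of underlying CVD risk. For the first three the plan notes that "the incidence of CVD and kidney disease outcomes are known to vary".
- **Multiplicity.** HTE tests are to be adjusted for the number of predefined HTE analyses; the method is not named.

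The plan does not say on which scale the predicted effect is measured. It gives no time horizon, no standardization step and no variance method for turning the fitted model into subgroup utility differences.

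**The concern.** In a Cox or parametric time-to-event model, a zero treatment-by-subgroup parameter means that the hazard or time ratio is the same in the subgroups. It does not mean that the utility difference is the same. For an overall comparison of two classes this matters less, because a ratio of 1 and a difference of 0 largely coincide. For an interaction they separate as soon as a class has an effect and baseline risk differs. The plan expects incidence to vary across its subgroups, and CVD-risk levels differ in baseline risk by construction.

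At stake is the conclusion about who gains more from which class. The plan defines the best treatment as the one that maximizes expected utility. Under a constant ratio, higher-risk patients can gain several times more utility while the interaction term shows nothing. Under a constant absolute gain, the interaction term can show heterogeneity that is absent on the utility scale.

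**Working it through.** **Inputs from the documents.** Four classes, hence C(4,2) = 6 pairs, which matches the plan. Subgroup contrasts against a reference: sex 1, race/ethnicity 4, age 3. The 0.05 level is stated for the omnibus test. The plan gives no event rate, effect size, cohort size or power for HTE, so there is no figure of its own to reproduce.

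**Assumptions.** One component event, coded as occurring or not by a fixed horizon; one class pair; proportional hazards; complete follow-up; no weighting; n patients per class per subgroup; two-sided 0.05. With a single component of weight w, the utility difference is w times the risk difference, so the comparison between subgroups is unchanged by w.

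**Formulas.** Treated risk p1 = 1 − (1 − p0)^HR; risk difference RD = p0 − p1. For the difference in RDs, SE = √[Σ p(1 − p)/n] over the four cells. For the log-HR interaction, SE = √[Σ 1/(n·p)] over the four cells.

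**Step 1: equal HR of 0.80, risks 5% and 15%.**
- 1 − 0.95^0.80 = 4.02%, so RD = 0.98 points.
- 1 − 0.85^0.80 = 12.19%, so RD = 2.81 points.
- The gap is 1.83 points, a 2.9-fold difference.
- The SE of the gap is 0.801, 0.566 and 0.400 points at n = 5,000, 10,000 and 20,000. So z = 2.28, 3.23 and 4.57, and power on the difference scale is 63%, 90% and 99.5%.
- The ratio test's null is true here, so it rejects at about 5%.

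**Step 2: equal RD of 0.98 points, same risks.**
- Treated risk in the high-risk subgroup is 14.02%, so HR = ln(0.8598)/ln(0.85) = 0.929, against 0.800 in the low-risk subgroup.
- ln(0.800/0.929) = −0.150. The SE is 0.108, 0.0766 and 0.0542, so |z| = 1.39, 1.96 and 2.77.
- The ratio test rejects 28%, 50% and 79% of the time, although the RDs are equal.

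A simulation with 1,500 data sets per scenario agreed: 64%, 91% and 99.5% for step 1, and 28%, 50% and 80% for step 2.

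**Step 3: multiplicity.** (1 + 4 + 3) × 6 = 48 contrasts before any for CVD risk. If Bonferroni were used, the level is 0.05/48 = 0.00104 and the critical z is 3.28.

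**Step 4: weaker settings, same formulas.** Each entry is for n = 5,000 / 10,000 / 20,000. False rejection is computed with the low-risk subgroup's RD applied to both subgroups.

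| Risks, HR | Power on difference scale under equal HR | False rejection by ratio test under equal RD |
|---|---|---|
| 5% vs 15%, 0.80, unadjusted | 63 / 90 / 99.5% | 28 / 50 / 79% |
| 5% vs 15%, 0.80, Bonferroni over 48 | 16 / 48 / 90% | 3 / 9 / 31% |
| 5% vs 10%, 0.80, unadjusted | 26 / 47 / 75% | 17 / 29 / 52% |
| 5% vs 10%, 0.90, unadjusted | 10 / 15 / 25% | 8 / 10 / 16% |

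**Step 5: where the two nulls agree.** With HR = 1, RD = 0 at every baseline risk: both nulls hold and both tests reject at 5%. With an effect, equal HR and equal RD can also coincide at two very different high and low risks, because RD rises and then falls with p0. At HR 0.80 it peaks at p0 = 1 − 0.8^5 = 67%, far above the risks assumed here. Hence the wording that both generally, rather than never, hold together.

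**The case against.** The strongest reply is that the plan never says HTE claims rest on the interaction coefficient. It names the subgroup target as a between-subgroup difference in predicted effects and fits effect-prediction models. Interaction terms can simply be how those predictions are produced, on whatever scale. Much of the fix below is compatible with that text. This stands: a reader might infer that the coefficient alone decides, or that the plan has declared equal utility differences as its subgroup null, and the documents state neither. The additive target is set for the class comparison, and its use for subgroups is an inference.

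The rationale for the subgroup analyses also points partly to relative effects. It speaks of different responses to therapy and of greater effectiveness in reducing endpoint risks at higher baseline risk. If that is the question, a constant hazard ratio is a fair answer of no heterogeneity. The text is also described as an overview of analyses exempt from IRB review, so some missing detail is to be expected.

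These replies do not remove the point. The only effect measures the modelling paragraphs produce are ratios, the only HTE device named is the interaction parameter, and nothing links either to the utility target. An analyst following the text could report a ratio-interaction p-value as the HTE result. If utility was meant, the text needs to say so; if relative effect was meant, the subgroup analysis does not address the plan's stated target.

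**Conclusion.** The point holds as a mismatch between the additive target and the ratio-scale subgroup method, with the subgroup scale left unstated. It should be changed, because following the text as written can give HTE conclusions that do not answer the plan's own utility question.

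A reader might go further and say that the test fails whenever baseline risk differs, or that it will give wrong conclusions. The documents do not support that. With no treatment effect the two nulls coincide, and with weak effects or modest risk differences the divergence is small. The rates above rest on assumed risks, effects and cell sizes, on one endpoint rather than the multi-endpoint utility, and on unweighted data. Inverse probability weighting and the planned multiplicity adjustment would lower both the false rejections and the power. They would not make the two nulls the same. Confidence in the mismatch is high; confidence in its size in this cohort is low.

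**What to change.** In the HTE paragraph, define the subgroup target as the between-subgroup difference in pairwise expected-utility differences at a pre-stated follow-up horizon. Compute it from the weighted model with its treatment-by-subgroup terms kept: predict expected utility under each class, standardized to the covariate distribution of each subgroup, then take pairwise differences within subgroups and compare them between subgroups. Test with a bootstrap or influence-function variance under the multiplicity adjustment already planned. Report the ratio-scale interactions alongside, labelled as heterogeneity of relative effect. They remain informative for that question, so they need not be dropped.

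The cost is wording and extra computation on data and models already planned, with no new patients. The small downside is that the result depends on the horizon, which must be fixed in advance, and that standard errors come from resampling or influence functions rather than from a printed coefficient.

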For this human subjects study, we will elicit patient preferences toward various treatment outcomes using a participatory ranking exercise and use these rankings to generate individually weighted composite outcomes. These composite outcomes (without any linked participant information) will be used for analyses within OLDW that will estimate patient-centered treatment effects of four different classes of second-line medications for Type 2 diabetes with respect to those composite outcomes specifically. The four drug classes that will be examined

are the GLP-1 receptor agonists (GLP-1RA), SGLT2 inhibitors (SGLT2i), DPP-4 inhibitors (DPP-4i), and sulfonylureas (SU).

Background (Include relevant experience, gaps in current knowledge, preliminary data, etc.):

Type 2 diabetes (T2D) is one of the most common and serious chronic health conditions in the U.S.¹ Optimal patient-centered T2D care is predicated on treating each patient with medications that are likely to yield the most benefit and risk the least harm, weighing the best available evidence against each patient's preferences and situation. While metformin is consistently recommended as the 1st-line drug in the management of T2D, there is less clarity regarding 2nd-line therapy as new drug classes were approved and introduced into practice,²⁻⁵ resulting in decisional dilemmas for patients and clinicians, and potential missed opportunities to select the drug that best optimizes the patient's health.

Cardiovascular disease (CVD), heart failure (HF), and chronic kidney disease (CKD) are leading causes of morbidity, mortality, and costs associated with T2D.⁶⁻⁹ Randomized controlled trials (RCTs) designed to evaluate the CV safety of T2D drugs revealed additional therapeutic benefits of glucagon-like peptide-1 receptor agonists (GLP-1RA) and sodium-glucose cotransporter 2 inhibitors (SGLT2i) with respect to CVD, HF, and CKD outcomes among patients at high risk for these events. However, it is unknown how each patient's preferences and values impact the comparative effectiveness of these drugs.

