A secondary analysis will be conducted under an as-treated approach, whereby patients will be censored upon discontinuation of the assigned treatment (no fills after 30 days beyond the dispensed pill count) or addition of another drug (i.e. another 2nd-line drug or insulin). To adjust for the likely informative censoring post-baseline, time-dependent propensity score models will be estimated and applied to dynamically reweight the population and account for time-varying confounding and informative loss to follow-up. The time-dependent propensity score models will be based on all prior covariate information up to that time point. This will address two concerns with use of observational methods for comparative effectiveness, immortal time bias⁴⁴ and time-lag bias,⁴⁵ as we will allow for time-dependent exposures and reweighting on time-conditional propensity scores.⁴⁶

Qualitative analysis of the accompanying interview: Interviews will be transcribed and analyzed according to a general thematic analysis approach (Braun & Clark, 2012) to identify patterns of meaning across patient interviews.

REFERENCES

1. CDC. National Diabetes Statistics Report, 2020. In. Atlanta, Georgia, U.S.A.: U.S. Department of Health and Human Services, Centers for Disease Control and Prevention; 2020.
2. American Diabetes Association Standards of Medical Care in Diabetes—2020. Section 9. Pharmacologic Approaches to Glycemic Treatment. *Diabetes Care*. 2020;43(Supplement 1):S98-S110.
3. NICE. National Institute for Health and Care Excellence Pathways: Managing Blood Glucose in Adults with Type 2 Diabetes. National Institute for Health and Care Excellence. <https://pathways.nice.org.uk/pathways/type-2-diabetes-in-adults>. Published 2019. Updated March 26, 2019. Accessed April 23, 2019.

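### Does a discontinuation rule worded as a pill count leave as-treated censoring undefined for products that are not dispensed as pills?

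*Combined protocol and SAP*

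**What the plan says.** The target-trial emulation in the OptumLabs claims data (OLDW) is described in the Data Analysis Plan after the weighted composite outcome has been defined. It compares four drug classes, and "The target parameter will be the six pairwise differences in the personalized utility function between the drug classes". The plan introduces the description with the words "We provide an overview of that analysis below" and notes that the claims analyses are exempt from IRB review.

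Two analysis sets are described. "Primary analyses will be conducted under an intention-to-treat approach", with intention defined as "a patient having two consecutive fills of the assigned drug"; patients then stay in follow-up until the study or their observation ends.

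The other set is secondary: "A secondary analysis will be conducted under an as-treated approach, whereby patients will be censored upon discontinuation of the assigned treatment". The parenthesis that follows gives the only definition of discontinuation in the document: "no fills after 30 days beyond the dispensed pill count". Starting another second-line drug or insulin is a separate reason for censoring and does not use the count. The same paragraph provides time-dependent propensity score models to deal with informative censoring.

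Nowhere does the document mention days' supply, units taken per day, or a rule for products that are not pills. It gives no dosage form for any of the four classes.

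**The concern.** The rule mixes units: a grace period in days is added to a count of pills. A pill equals a day only with once-daily dosing, so a literal calculation would give different grace periods to patients on different dosing frequencies.

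Products without pills raise a second doubt. Suppose one class, such as the GLP-1RA, is mostly injected. That is an assumption from general knowledge, not something the documents state. A pill count would then not exist for that arm, and each class appears in half of the pairwise contrasts.

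The discontinuation date is the censoring date in the as-treated analysis. If it were set differently by class merely because of how the product is packaged, exposure time and events would be counted differently between arms. The reweighting would not repair this, because a censoring model needs a defined censoring event and cannot supply one.

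**Working it through.** The documents report no number that depends on this rule, so there is nothing to reproduce. The check is whether the wording allows two workable readings that give different censoring dates.

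**Inputs.** The 30-day allowance comes from the as-treated paragraph of the Data Analysis Plan. All fill sizes below are assumptions chosen for illustration; the documents give none.

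**Formulas.** Let U be the units dispensed and D the days they last at the prescribed frequency.

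- Supply reading: censoring day = D + 30, so the grace after supply ends is (D + 30) − D = 30 for every fill.
- Unit-as-day reading: censoring day = U + 30, so the grace is U + 30 − D.

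| Assumed fill | U | D | Censoring day, supply reading | Grace | Censoring day, unit-as-day reading | Grace |
|---|---|---|---|---|---|---|
| Once daily | 30 | 30 | 60 | 30 | 60 | 30 |
| Twice daily | 60 | 30 | 60 | 30 | 90 | 60 |
| Twice daily, long fill | 180 | 90 | 120 | 30 | 210 | 120 |
| Weekly unit | 4 | 28 | 58 | 30 | 34 | 6 |
| Weekly unit, long fill | 12 | 84 | 114 | 30 | 42 | −42 |

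**Reading the table.** The readings agree only when one unit lasts one day. In the last row the unit-as-day reading ends exposure on day 42 of an 84-day supply, 42 days before the patient runs out. That cannot be what a rule with a 30-day allowance *beyond* the dispensed quantity means. The supply reading is also the only one in which the sum has a consistent unit. It needs D and not U, so it applies to a non-pill product exactly as it does to a tablet.

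**Contrasts.** Four classes give 4 × 3 / 2 = 6 pairs, and any one class enters 3 of them. The as-treated paragraph does not list its contrasts; carrying the six over is the natural inference. Saying that three of them lack a defined censoring date requires the literal reading and also the outside assumption about dosage form. Under the supply reading the number of undefined contrasts is 0.

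**Reach.** The primary analysis rests on two fills and continued follow-up, so the count does not enter it. The second as-treated censoring trigger does not use it either.

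**The case for a change.** The best case for a change is that the text really is silent. The intended conversion has to be inferred, no fuller specification is supplied with this document, and one sentence written before the outcome data are analysed would remove a discretionary choice at almost no cost. For products in other forms, the duration of a fill may also be harder to establish than for tablets. A check of recorded supply against observed refill intervals would show whether the GLP-1RA arm is handled fairly.

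The silence stands, and so does the point that a fuller specification has not been shown to exist. The rest carries less weight. Discretion matters when two or more defensible choices are open, and here the alternative gives results nobody would accept. The proposed sentence would record the definition that analysts would use anyway. The supply check answers a data-quality problem that no part of the documents describes, and a sentence in this plan would not cure such a problem if it existed. This document is the IRB protocol for a ranking and interview study of 25 people; the absence of programming-level exposure rules from its summary of an exempt claims analysis is weak evidence of a defect.

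**Conclusion.** No change to the plan is called for. The phrase is loose wording for the period that the dispensed supply lasts, and analysts following the plan would apply it that way and obtain a uniform 30-day allowance for all product forms. The larger departures in the illustration, a grace of 120 days or of −42 days, belong to a reading that is not a realistic option; they do not estimate any error. No bias and no undefined contrast has been shown, and the primary analysis is untouched.

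This conclusion assumes that analysts read the count as a supply period and that the claims data allow the duration of each fill to be obtained for every product. The documents do not address the second assumption. If it failed for one class, the resulting problem would lie in the data of the secondary analysis and not in this wording.
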